11.2 Data Analysis Plan

Defining the Study Population and Treatment Groups - The primary analysis is by intention-to-treat, including all randomized participants in their assigned treatment arm and including all events observed during the study irrespective of adherence to assigned treatment. When participants withdraw or go “off study,” follow-up will be censored at the date of the last visit. Exploratory “per-protocol” analyses and analyses in subgroups defined by level of adherence to study treatment will be undertaken as well, but are not considered part of the confirmatory analysis plan.

Every effort will be made to establish eligibility prior to enrollment and randomization; however, a few enrolled participants may subsequently be found not to meet all enrollment criteria. Most such individuals will be at increased risk for incident diabetes even though some eligibility criteria were not assessed or met. Thus, the primary analyses will include all randomized participants. If more than 1% of those randomized do not meet all eligibility criteria, which is an unlikely scenario, we will perform sensitivity analyses to assess the impact of excluding those individuals.

Baseline Characteristics – Although the randomization procedure should produce balanced treatment groups, relevant demographic (age, gender, race, ethnicity) and baseline clinical characteristics (e.g., BMI, physical activity, family history of diabetes, and 25OHD concentration) of participants will be compared across groups to characterize study participants and to document the success of the randomization procedure. Standard parametric and nonparametric statistical techniques will be used to test for differences in the distributions of baseline characteristics between treatment groups. Statistical significance will be determined from two-sided tests with an alpha level of 0.05. The large size of the trial and the stratification by BMI and race make it likely that differences in the distributions of these potential confounders between treatment groups, if statistically significant, will not be clinically significant.

Primary Outcome – The primary endpoint (outcome variable) is “*time to progression to incident diabetes.*” For most participants, incident diabetes will be diagnosed at one of the regularly scheduled study visits, which will occur every 6 months. In some cases, however, participants will notify study personnel that they have received a diagnosis of diabetes, or been placed on diabetes medication, by their personal physician. In such cases, every effort will be made to assess whether the participant has met the study criteria for incident diabetes. When participants have been placed on a diabetes medication and the diagnosis cannot be confirmed by D2d laboratory criteria or adjudicated by the clinical outcomes committee, the participant will be considered to have not reached the primary study

outcome and follow-up for incident diabetes will continue per the-intent-to treat principle. Sensitivity analyses will be performed that include these occurrences (i.e., a diabetes-specific medication is prescribed but a D2d-diagnosis of diabetes is not made) as cases of incident diabetes.

Statistical Methods - Since the exact time of progression to incident diabetes, defined as the date on which the criteria for incident diabetes would have been met if laboratory tests had been performed, will be unknown for participants who receive a diagnosis of incident diabetes at a regularly scheduled study visit, one could consider statistical methods for interval-censored data for the analysis of the time-to-event variables.²⁷⁷ However, subjects whose diagnosis is initiated by their personal physician will not have a diagnosis date corresponding to a regular visit, and participants will have variable visit schedules. Thus, we have chosen instead to use standard methods for analysis of right-censored time-to-event data, using the incidence date defined in Section 9.1 for the primary outcome. The interval-censored approach and the right-censored time-to-event approach would give similar estimates and standard errors for treatment effects, because the change in approach would have similar effects on the estimated time-to-event distributions in the two treatment groups. Moreover, the notion that each individual participant has a true exact date of onset of diabetes is a somewhat artificial concept, in that an individual will not consistently meet the diagnostic criteria on successive days as they transition from pre-diabetes to incident diabetes.

Kaplan-Meier estimates of “time to confirmed diabetes” distributions will be calculated for each treatment group. The log-rank test will then be used to perform an unadjusted comparison of the time-to-event distributions in the two treatment groups. Follow-up of participants who withdraw or are lost to follow up will be “censored” on the date of their last follow-up visit. All p values examined for statistical significance will be two tailed, and p-values below 0.05 will be considered statistically significant. Cox proportional hazard models²⁷⁸ will be used to calculate an estimate of the adjusted hazard ratio. To construct the model for the adjusted analysis, we will first construct a regression model that does not include the indicator for treatment group. Age, race, ethnicity, BMI, and other variables (fasting glucose, 2-hr glucose, HbA1c and 25OHD) to be specified a priori will be forced into the model. Variables will then be added in a step-up fashion from a list of candidates selected a priori. Covariates making a statistically significant contribution to the proportional hazards regression model will be included in the multivariate model. When the step-up procedure has been completed, the covariate for treatment group will be added to the model. The regression coefficient for treatment group in this multiple regression model will be the adjusted estimate of the log hazard ratio.

Subgroup Analyses - Variability of response to vitamin D supplementation will be assessed by pre-specified analyses in participant subgroups defined by *baseline* variables, e.g., race (self-reported definitions of White, vs. non-White e.g. Black/African American, American Indian, Alaska Native); ethnicity (Hispanic vs. Non-Hispanic); BMI (two groups based on median value); waist circumference (two groups based on median value);¹⁸⁷ age (two groups based on median value); geographic location (two groups, above or below 42° latitude), calcium intake and 25OHD concentration (two groups based on median value). Subgroup analyses by clinically applicable cutoffs will also be done (e.g. BMI as normal weight, overweight or obese; 25OHD concentration by IOM cutoffs). Each analysis of participant subgroups will include a test for interaction. Effect modification will be claimed only if the test for interaction reaches statistical significance. These analyses, although pre-specified, are considered exploratory as the study is not powered for such analyses and multiple comparisons must be considered when interpreting findings that are nominally statistically significant. We will also assess variability of response to vitamin D supplementation by “per-protocol” and “on-treatment” analyses, where treatment is defined by adherence based on pill count or achieved 25OHD concentration. These analyses will also be considered to be exploratory.

Missing Data - Missing data are inevitable in clinical research. Every effort will be made to minimize missing data in D2d. The primary methods of data analysis assume that censoring for time-to-event variables is non-informative. However, as recommended in the recent report of the Institute of

Medicine, we will perform sensitivity analyses to assess the degree to which the results are sensitive to the validity of the assumptions of non-informative censoring or non-informative missingness.

Data Monitoring Plan – Methods for interim analysis of accumulating data will be reviewed and approved by the D2d DSMB, which will regularly review accumulating safety and efficacy data to assure that continuation of the study remains scientifically and ethically appropriate. As a specific part of this monitoring activity, a single formal interim analysis of the accumulating primary endpoint data will take place when 70% of the expected events have accrued. The stopping boundary for the interim analysis will be based on the Peto-Haybittle approach.^{279,280} With this stopping boundary, the nominal P value representing statistical significance will be 0.001, corresponding to a Z score of 3.09.

The D2d coordinating center will prepare the reports on behalf of the DSMB, whose members will review the data and advise the sponsor (NIDDK) whether (1) there is evidence that the intervention is clearly better or worse than placebo in relation to the primary outcome, and (2) the DSMB recommends a change in the study plan based on safety considerations.

Seasonal and Geographic Variability – Given that the cohort will be recruited at a constant rate throughout the calendar year and outcomes will be determined every 6 months, the potential for seasonal variability confounding the association between vitamin D supplementation and outcomes is low. We will test this assumption in the analyses, and if needed, we will adjust for the month of the year at entry into the study. All analyses will adjust for site, as routinely done in multicenter studies, which will also approximate latitude at each of the participating sites. Given the age group, we anticipate few participants moving residence during the study.

12. FUNDING, STUDY ORGANIZATION, ADMINISTRATION AND GOVERNANCE

12.1 Sponsors

The planning phase of D2d was funded by the National Institute of Diabetes and Digestive and Kidney Diseases (NIDDK) of the National Institutes of Health (NIH) through the Multi-Center Clinical Study Implementation Planning Grant (U34) to Tufts Medical Center in Boston, Massachusetts (U34DK3491958). The conduct of D2d is supported primarily by NIDDK and the Office of Dietary Supplements through the U01 Multi-Center Clinical Study Cooperative Agreement (U01) to Tufts Medical Center (U01DK098245), which has established sub-award agreements with each collaborating clinical site and core units (e.g. Central Laboratory, drug distribution center) to reimburse each site and core unit for their activities related to D2d. Funding is also provided by the American Diabetes Association (1-14-D2d-01). Educational materials are provided by the National Diabetes Education Program. The primary funding agency (NIDDK) and the study investigators work as partners; however, the primary responsibility for the D2d study planning and conduct is with the study's Principal Investigator and the CC. Representatives from NIDDK participate in all phases of planning, development of the protocol, development of policies and procedures, implementation and monitoring of study performance and safety, data analyses and interpretation and dissemination of study findings.

12.2 Organizational Overview

Overall study leadership is provided by the Steering Committee while the Executive Committee acts as the operational arm of the Steering Committee. The D2d Coordinating Center (CC) is established in the Division of Endocrinology at Tufts Medical Center. The CC provides overall study organization and administration, and manages day-to-day operations by working directly with the collaborating sites, other study core units and study committees and subcommittees. The CC implements the study protocol; oversees the development of the Manual of Procedures; monitors participant recruitment and treatment delivery; evaluates data collection and management; oversees quality assurance procedures; monitors participant safety; and implements changes and enhancements to the study as recommended by the Steering Committee. The CC also develops the data collection processes, performs data monitoring, data cleaning and analyses and contributes to manuscript writing. The *Drug Distribution Center*, located at the VA Cooperative Studies Program, Clinical Research Pharmacy Coordinating Center, conducts the randomization and distribution of study drug to the sites. The *Central Laboratory*, located at the University of Vermont in Burlington, Vermont, coordinates collection of study specimens from collaborating sites, conducts laboratory measurements and serves as a central repository for short and intermediate-term storage of human blood and urine samples. Long-term storage of human blood and urine samples will be transitioned to the NIDDK Central Repositories.

12.3 Study Leadership and Governance

12.3.1 Executive Committee (EC)

The EC acts as the operational arm of the Steering Committee (SC) and makes scientific, administrative and fiscal decisions, on behalf of the SC, for day-to-day operational issues requiring prompt action. The committee develops timelines for the accomplishment of tasks, appoints (and disbands) subcommittees as the need arises and selects subcommittee members and chairs, presents information to the sponsor, and develops Steering Committee meeting agendas.

12.3.2 Steering Committee (SC)

The SC provides scientific leadership for the study. The committee works closely with its operational arm, the EC, and the SC subcommittees. The committee reports to the primary study sponsor (NIDDK), via the EC. The committee is comprised of all standing members of the EC plus the Principal Investigator from each collaborating site and the Central Laboratory

12.3.2.1 Steering Committee Subcommittees

There are 7 standing subcommittees, which are established to monitor specific components of the study conduct and to provide periodic status reports to the Steering and Executive Committees.

The following subcommittees have been established:

Conflict of Interest Subcommittee (CIS): The subcommittee reviews all conflict of interest forms in which there has been a disclosure. The committee will determine if a potential conflict of interest exists, and will develop and implement a management plan that will specify the actions that have been and/or will be taken to eliminate or limit the potential impact of such conflict(s) on the study's credibility. The subcommittee works closely with the sponsor to evaluate and mitigate conflicts of interest

Recruitment and Retention Subcommittee (RRS): The subcommittee reviews and approves the collaborating sites' recruitment plans prior to the start of the study and monitors recruitment progress and retention and adherence to study procedures. Rates of participant retention and prompt and complete data capture will serve as quality measures of performance by the sites. Pre-specified site-specific targets for optimal performance are defined and should be met to achieve high quality of trial conduct. The subcommittee reviews these measures regularly and makes recommendations (general or site-specific) to improve these rates and ensure that sites meet their target recruitment/retention goals. The subcommittee makes recommendations to the Executive Committee regarding the need for additional sites, if recruitment is slower than anticipated.

Support and Education Subcommittee (SES): The subcommittee develops the Support and Education Program that will be implemented during the study. The subcommittee reviews and approves the education materials on the current lifestyle recommendations for prevention of type 2 diabetes that will be provided to all participants at baseline. The subcommittee also develops program themes and content for use during the SEP group meetings that will be held at each site twice a year. The goals of the SEP meetings will be: (1) to provide participants with up-to-date information on the lifestyle recommendations for the prevention of type 2 diabetes and (2) to promote participant retention. Towards these goals, the SES works closely with the RRS.

Research Coordinators Subcommittee (RCS): The subcommittee is comprised of the research coordinators from each site and representatives from the CC. The major objective of the subcommittee is to assure communication among the sites with respect to overall study coordination and share best ideas and problem solve. The coordinators are closest to the day-to-day issues at the sites; therefore, they are expected to be an invaluable resource to the study and are encouraged to make recommendations regarding the study conduct to the Steering and Executive Committees for review and consideration. The Chairperson of the RCS is a member of the EC.

Safety & Outcomes Subcommittee (SOS): The subcommittee implements the Data Safety Monitoring Plan. The subcommittee reviews all serious adverse events (SAE) and unanticipated problems (UAP) as they are reported, reviews periodic safety reports of all adverse events (AE) and oversees study safety. The subcommittee chair or designee assesses each SAE and UAP to determine if immediate action is required in response to the event. The subcommittee meets three

times a year (or more frequently if needed) by conference call. During these meetings, the subcommittee discusses SAE, UAP and summary reports of non-serious AE. The subcommittee also evaluates whether there is any clustering of AEs, SAEs or UAPs by clinical site. The subcommittee remains masked to patient treatment group during these evaluations. The subcommittee considers whether changes in the protocol (monitoring, consent process, etc.) are indicated based on the occurrence, frequency, or severity of AE, SAE or UAP and provides its recommendations to the Steering and Executive Committees for further discussion and subsequently to the DSMB for approval and implementation. The subcommittee also provides adjudication for secondary outcomes.

Ancillary Study Evaluation Subcommittee (ASES): The subcommittee is responsible for establishing and overseeing the Ancillary Studies Policies and Procedures and ensuring that the policy is followed. The subcommittee is responsible for evaluating ancillary study applications and making recommendations to the Steering Committee regarding the proposals and monitors progress of approved ancillary studies.

Publications & Presentations Subcommittee (PPS): The subcommittee develops and oversees the policies and procedures by which D2d investigators will interpret data analyses and will coordinate publications and presentations of study results. The subcommittee is responsible for establishing and overseeing the Publications and Presentations Policy and ensuring that the policy is followed. The subcommittee reviews and approves all publications and presentations related to the D2d study, including those from ancillary studies, prior to submission. The subcommittee monitors the progress of all proposed manuscripts to ensure prompt completion and publication.

12.3.3 Clinical Outcomes Committee (COC)

The committee, which is independent of the D2d Study Group, is formed to review and adjudicate the diagnosis of diabetes that is made outside of the D2d study or initiation of diabetes-specific medication (for any reason) when study-specific glycemic data are not available. The COC is composed of clinical diabetes experts who have no real or perceived conflict of interest related to the D2d study, D2d Study Group, sponsor or study core units.

12.4 Role of Industry

Industry may contribute resources to the study and will be acknowledged appropriately; however, industry will play no role in the design and conduct of the study, data analysis, interpretation or publication of study results.

SUPPLEMENTS AND APPENDICES

1 OVERVIEW & ADMINISTRATIVE INFORMATION

The present version 2 of the Statistical Analysis Plan (SAP) corresponds to version 1.9 of the protocol and associated Manual of Procedures.

The Statistical Analysis Plan (SAP) includes statistical hypotheses, outcome measures, methods for the primary outcome analysis and subgroup analyses. The SAP follows the outline and general principles outlined in the Data Analysis Plan section of the protocol; however, the SAP provides more detail compared to the protocol while previously proposed analyses that are of questionable value have been removed.

2 STUDY POPULATION & TREATMENT GROUPS

Defining the Study Population and Treatment Groups - The primary analysis is intention-to-treat (ITT), including all randomized participants in their assigned treatment arm and including *all diabetes events observed during the study*, irrespective of adherence to assigned treatment. For all participants, follow-up will be censored at the date of the last assessment for incident diabetes (see section 4).

Every effort has been made to establish eligibility prior to randomization; however, 13 participants (0.05% of the cohort) have been subsequently found not to meet all eligibility criteria. Some of these participants were ineligible because of a safety exclusion criterion and are not on study pills. Consistent with the ITT principle, participants who did not meet eligibility criteria will be included in all analyses. This proportion (0.05%) is considered small and, consistent with the data analysis plan in the protocol, does not warrant sensitivity analyses to assess the impact of excluding those individuals from the analyses.

3 OUTCOME VARIABLES

3.1 Primary outcome

The primary endpoint is time to incident diabetes, as described in the protocol and Manual of Procedures 18.

Cases of diabetes diagnosed outside of D2d (i.e., during routine clinical practice) among “inactive” participants that are discovered incidentally by D2d research staff will not count as diabetes cases and will not be included in the primary analysis.

3.2 Secondary outcomes

A number of secondary outcomes will be analyzed to clarify the interpretation of the results of the primary analysis. Some of these analyses (e.g., insulin secretion) will not be presented in the main manuscript but in separate publications.

3.2.1 Secondary outcomes – related to the primary outcome: continuous variables

- HbA1c (measured at baseline, semi-annually)
- FPG (baseline and semi-annually)
- 2hPG (baseline and annually)
- Insulin secretion, Insulin sensitivity and Disposition Index (indices from OGTT; baseline and annually)

3.2.2 Secondary outcomes – independent of the primary outcome: continuous variables

- Blood pressure (baseline and semi-annually)
- Cardiovascular risk factors: cholesterol profile, C-reactive protein, urine albumin excretion (baseline, M12 and M24)
- Atherosclerotic Cardiovascular Disease (ASCVD) ACC/AHA composite risk score (baseline, M12, M24)

3.3 Explanatory outcome: continuous variable

- 25OHD concentration (baseline, M12 and M24)

3.4 Safety outcomes: binary variables

- Hypercalcemia, as defined in the protocol and Data Safety and Monitoring Plan
- Hypercalciuria, as defined in the protocol and Data Safety and Monitoring Plan
- Nephrolithiasis, as reported by clinical sites and Data Safety and Monitoring Plan

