24. Any other unstable active medical condition (including but not limited to liver disease, wasting illness, AIDS, tuberculosis, oxygen-dependent chronic obstructive pulmonary disease, organ transplant, Cushing's syndrome) that in the opinion of the site investigators would impede competence or adherence with study procedures or increase risk. [Safety, adherence, plasma 25OHD may decrease as an acute-phase response^{254,255}] Such conditions will be assessed based on self-report and/or review of medical records (if available).
25. Uncontrolled hypertension (systolic blood pressure > 160 mm Hg or diastolic blood pressure > 100 mm Hg). [Safety]
26. Poor venous access. [Safety]

Laboratory Evaluation

27. Serum liver transaminase (ALT or AST) higher than 3 times the normal range for the clinical site's laboratory [Safety]
28. Anemia (hematocrit < 32 for women, < 36 for men), whole blood transfusion (within 6 months of screening) or chronic requirement, whole blood donation (within 3 months of screening) or other condition (hemolysis, hemoglobinopathy) rendering HbA1c results unreliable as indicator of chronic glycemia. [Interference with outcome assessment] Participants who donate platelets are

not excluded. Whole blood transfusion or donation does *not* exclude participant, but screening and study visits need to be timed appropriately.

29. Low platelet count (< 50,000). [Safety for blood draws]
30. Chronic kidney disease, defined as estimated glomerular filtration rate [GFR] < 50 mL/min, from creatinine measured at the clinical site's laboratory and GFR calculated centrally. [Vitamin D homeostasis changes as GFR declines. These changes start when GFR falls around 40-60 mL/min per 1.73 m².^{256,257} The planning committee selected 50 mL/min as the exclusion cutoff to ensure that participants maintain GFR > 40 mL/min during the study] Please note: to prevent potential confusion, GFR units will be denoted as mL/min throughout the protocol and associated documents.
31. Hypercalcemia, defined as serum calcium concentration greater than or equal to the upper limit of normal, measured at the clinical site's laboratory. [Safety]
32. Hypercalciuria, defined as spot urine (morning void) calcium-creatinine ratio > 0.275.²⁵⁸ [Safety]

Other

33. Participation (within 30 days of screening) in another interventional research study. [Conflict, "contamination"]

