8.2.2 Safety Laboratory Tests during the Study

To monitor safety, the following laboratory tests will be drawn and analyzed at each *site's clinical laboratory* at M03, M12, at yearly visits thereafter, and as needed to evaluate symptoms and/or physical signs. Results will be provided to participants and their health care provider(s).

- Serum calcium
- Serum creatinine and estimated creatinine clearance (GFR, calculated centrally)

To monitor safety, the following laboratory test will be analyzed at the Central Laboratory at BAS, M03, M12, at yearly visits thereafter, and as needed. The Central Laboratory will analyze the urine calcium-to-creatinine (instead of the site's clinical laboratory) because: (1) this variable also serves as a safety outcome of interest and would be important to standardize its measurements; (2) the result does not need to be communicated back to the participant urgently. Results will be reported to the clinical site and also provided to participants and their health care provider(s).

- Urine calcium-creatinine ratio

To monitor safety, the following laboratory test will be drawn and analyzed at each *site's clinical laboratory.*

- Pregnancy test for women of reproductive potential who report missing two consecutive menstrual periods *based on the participant's typical menstrual cycle*.

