During the study, to minimize the occurrence of “expected” AE and overall risk, the following measures will be taken:

Intervention

- Serum calcium and creatinine (GFR), and urine calcium excretion will be monitored at regular intervals.
- At each contact (phone or visit), participants will be questioned in regards to changes in their health or medications (prescription or non-prescription, including supplements).

Outcome Measures

- For all blood draws/catheter insertion, research staff will follow the usual sterile techniques and only experienced personnel will perform the procedure to minimize discomfort, bruising and risk of infection or bruising.
- To minimize the risk of anemia from repeated blood draws, the smallest amount of blood required for each testing procedure will be drawn.

Trial Participation

- A site study physician (or his designee) will be available at all times to evaluate and provide the necessary medical intervention in the event of an adverse event, or make a referral for the appropriate care.
- Risk to patient confidentiality is minimal because all study records are confidential within the study staff environment. Although the consent form will specify what protected health information will be collected and with whom it will be shared, an authorization form in addition to the consent form will be signed by participants from institutions that require a separate document in accordance with their interpretation of the Health Insurance Portability and Accountability Act (HIPAA) guidelines. Safety precautions and encryption of data will ensure that electronic systems do not pose a risk to participant confidentiality. Study results will be published, but participant identity will not be revealed in any articles or scientific presentations and records will be kept as required by federal and state laws and regulations.

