6 SAFETY ANALYSES

The safety analyses will examine the effect of vitamin D supplementation on the following safety outcomes.

- Hypercalcemia
- Hypercalciuria
- Nephrolithiasis

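### SAP 3.4 and 6 analyse serum calcium and the urine calcium-creatinine ratio only as yes/no outcomes; a supportive analysis of the measured values should be added

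*SAP*

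**What the plan says.** SAP 3.4 is headed "Safety outcomes: binary variables". Two of its three entries are "Hypercalcemia, as defined in the protocol and Data Safety and Monitoring Plan" and "Hypercalciuria, as defined in the protocol and Data Safety and Monitoring Plan"; the third is nephrolithiasis. SAP 6 reads "The safety analyses will examine the effect of vitamin D supplementation on the following safety outcomes" and repeats the three names, without a test, model, effect measure or interval. Neither serum calcium nor the urine calcium-creatinine ratio appears among the continuous outcomes in SAP 3.2 and 3.3, or in the mixed-model analyses of SAP 5.

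The protocol collects the numbers:

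- Serum calcium is measured at screening, and the urine ratio at baseline (8.2.1).
- Both are measured at M03, at M12 and yearly after that (8.2.2), and they continue after a diabetes diagnosis (8.2.3).
- Section 10.1.2 says "Serum calcium and creatinine (GFR), and urine calcium excretion will be monitored at regular intervals".
- Serum calcium is assayed at each site's laboratory and the urine ratio centrally. One reason that 8.2.2 gives for the central assay is that "this variable also serves as a safety outcome of interest and would be important to standardize its measurements".

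The only numeric cut-offs in the current protocol text are entry exclusions (5.2): "serum calcium concentration greater than or equal to the upper limit of normal" and "spot urine (morning void) calcium-creatinine ratio > 0.275". The SAP refers the on-study definitions to the protocol and the Data Safety and Monitoring Plan, which is not among the documents reviewed.

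**The concern.** Evaluating safety is one of the trial's stated objectives (Protocol 3.1), and these two biomarkers lie closest to the known risks of the intervention. Protocol 10.1.1 labels the intervention-related events uncommon, and 5.2 excludes people already above either cut-off, so the yes/no comparisons may rest on few events.

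A threshold outcome records who crossed and ignores how far everyone else moved. If vitamin D shifts calcium upward modestly in most participants, comparing a few crossings could miss it, although the values that would show it are in the database. The SAP already has a repeated-measures model for blood pressure, lipids and C-reactive protein, but these two measures get none.

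**Working it through.** **The plan's own power figure.** The documents state none for any safety outcome. The one they give, for the primary outcome, reproduces by the Schoenfeld formula: 4 × (1.960 + 1.282)² / (ln 0.75)² = 42.03 / 0.08276 = 508 events, as in Protocol 11.1.

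**Inputs from the documents.** 2,382 participants randomised 1:1, so 1,191 per arm; two-sided alpha of 0.05.

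**Assumptions, because the documents are silent.** Roughly normal values; the same shift in everyone in the active arm; one time point; no attrition unless stated. The exceedance rate q in the placebo arm runs from 0.5% to 20%, and the shift d from 0.10 to 0.30 SD.

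**Step 1: information kept by a yes/no split.** For a small shift, the information relative to comparing means is φ(z)² / [q(1 − q)], where z is the normal quantile that leaves q above it. At q = 1%, z = 2.326 and φ(z) = 0.02665, so 0.02665² / 0.0099 = 0.072 is kept and 92.8% is lost.

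| q | kept | lost |
|---|---|---|
| 0.5% | 0.042 | 95.8% |
| 1% | 0.072 | 92.8% |
| 5% | 0.224 | 77.6% |
| 10% | 0.342 | 65.8% |
| 20% | 0.490 | 51.0% |

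**Step 2: power with 1,191 per arm.** For the measured value, power = Φ(d / √(2/1191) − 1.960). At d = 0.15 this is Φ(0.15/0.04098 − 1.960) = Φ(1.70) = 0.955. For the split, the active-arm rate is 1 − Φ(z − d). At q = 1% and d = 0.15 that is 1.48%, and the two-proportion test has power 0.18.

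| d | q = 0.5% | q = 1% | q = 5% | measured value |
|---|---|---|---|---|
| 0.10 SD | 8% | 10% | 22% | 68% |
| 0.15 SD | 13% | 18% | 44% | 96% |
| 0.30 SD | 41% | 61% | 97% | over 99.9% |

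With the synopsis maximum of 15% attrition (1,191 × 0.85 = 1,012 per arm) and d = 0.15, the measured value has 92% power, against 11%, 16% and 39% for the split.

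**Step 3: do repeated visits rescue the split?** A simulation compared any exceedance in four visits with the mean of four visits, at an assumed within-person correlation of 0.3 to 0.7. The loss was 96–97% at an ever-exceed rate of 0.5%, 80–86% at 5% and 69–77% at 10%. They do not.

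**Step 4: the opposite pattern.** Suppose that 2% of the active arm shift by 3 SD and the rest not at all. The mean moves by 0.02 × 3 = 0.06 SD, and the comparison of means has 29% power. At q = 0.5% the active-arm rate becomes 1.8%, and the split has 85% power; at q = 1% it has 79%. If the 2% shift by 2 SD, the split has about 33% and the mean 16%.

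**The case against.** The strongest reply is that the safety question concerns who crosses a threshold. Protocol 7.5 ties permanent discontinuation of study pills to hypercalcemia and hypercalciuria, and 10.1.2 describes predisposed people. Step 4 shows that, for harm confined to such people, the yes/no outcome is the better instrument and the mean can miss it. This stands, and it is why the binary outcomes must stay and the measured values only supplement them.

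A reader might go further than the documents allow in four ways:

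- *That the plan discards 78–96% of the information as a matter of fact.* That range needs exceedance of 5% down to 0.5%, plus normality and a common shift. The documents give no rate, and they say uncommon, not rare. At 20% exceedance the loss is 51%.
- *That the planned comparison would probably be null even if calcium clearly rose.* At 0.30 SD the split has 61% power at 1% exceedance and 97% at 5%. The worry applies to modest shifts or very low rates.
- *That Protocol 8.2.2 promises an analysis of the measured ratio.* It does not. Standardised measurement also serves a common threshold across sites. The text shows that the ratio matters, not that a commitment was broken.
- *That using binary outcomes is an error.* It is not. What is missing is a supplementary analysis.

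It can also be said that SAP 6 gives no effect measure or interval even for its listed outcomes, and that intervals there would guard against reading a null as reassurance. That is true and worth doing, but it would not recover the information lost by the split.

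Two practical objections also stand. Serum calcium comes from local laboratories, so a model of raw values needs a site term. Stopping pills under Protocol 7.5 dilutes an as-assigned estimate at later visits; the power figures above ignore this.

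**Conclusion.** The point holds as an omission. Both calcium measures enter the SAP only through a cut-off, although the protocol collects the values repeatedly and treats the urine ratio as a safety outcome in its own right. For a common shift in roughly normal values at one time point, the split loses at least half the information at every exceedance rate examined up to 20%, and over nine tenths at 1% or below. A shift of 0.10 to 0.15 SD could well be missed at exceedance of 5% or less; a shift of 0.30 SD much less so, except at the lowest rates. The rates, the distribution and the shift sizes are all assumed. Under a tail-only effect the ranking reverses. Nephrolithiasis is an event and is unaffected. The supportive analysis should be added; nothing already planned needs to be withdrawn.

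**What to change.** Keep the three binary outcomes. Add to SAP 6, labelled as supportive:

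- the between-arm difference with 95% CI in serum calcium and in the log urine calcium-creatinine ratio, over M03, M12 and the annual visits;
- the linear mixed model of SAP 5, with the pre-randomisation value as covariate (screening for serum calcium, baseline for the urine ratio);
- adjustment for site, which matters most for the locally assayed serum calcium;
- all randomised participants as assigned.

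The cost is a few lines of SAP text and two models on data already collected, with no new visits or assays. The downsides are small and should be stated alongside the result: a mean shift is not a clinical event, a mean can miss harm confined to the tail, and as-assigned estimates are diluted where study pills are stopped.
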